4.2.4.5 Laboratory evaluation

Unless otherwise specified, laboratory data obtained after the start of study medication dosing up to and including 4 days (30 days for liver function laboratory tests) after the last short-term double-blind dosing date (or up to the start of the long-term treatment period, whichever comes first) will be considered as obtained during the short-term double-blind treatment period. For studies with a follow-up period, laboratory data obtained from the day after the last study medication + 4 days (30 days for liver function laboratory tests) up to the last visit date of the follow-up period will be considered as obtained during the follow-up period.

For liver safety, a summary of proportion of subjects with elevated liver test including elevated aminotransferases (AT; alanine aminotransferase [ALT] and/or aspartate aminotransferase [AST]) and total bilirubin (see Appendix 3 for definition) will be provided. In addition, a summary of proportion of subjects with elevated liver tests and/or reported AE of hepatic disorder will also be provided. For those summaries, liver test data obtained after the start of study medication dosing up to and including 30 days after the last short-term double-blind dosing date (or up to the start of the long-term treatment period, whichever comes first) will be considered as obtained during the short-term double-blind treatment period.

For self-monitored blood ketones that are not associated with an event sent for DKA adjudication, number of subjects with at least one self-monitored blood ketone result and number of subjects with at least one self-monitored blood ketone result elevated (defined as beta-hydroxybutyrate > 3.0 mmol/L) will be summarized by treatment group. In addition, the proportion of subjects with at least one self-monitored blood ketone result elevated will be analyzed using a logistic regression procedure, adjusting for baseline HbA1c, percent of insulin reduction at start of treatment from baseline, age, gender and randomization strata.

Marked laboratory abnormalities

Laboratory abnormalities will be evaluated based on marked abnormality (MA) values. The pre-defined criteria for marked abnormalities are detailed in Appendix 9.3. If both the baseline and on-treatment values of a parameter are beyond the same MA limit for the parameter, then the on-treatment value will be considered a MA only if it is more extreme (farther from the limit) than was the baseline value. If the baseline value is beyond the low MA limit, and the

post-baseline value is beyond the high MA limit (or vice-versa), then the post-baseline value will be considered a MA.

Laboratory abnormalities occurring during the short-term double-blind treatment period will be summarized by treatment group. In the short-term double-blind treatment period the summaries will be presented for both the primary and sensitivity safety analyses. The direction of change (high or low) in MA will be indicated in the tables.

Additionally, for each subject with a MA for a parameter, all the subject's values of that parameter over the short-term double-blind treatment period and the follow-up period, where applicable, will be listed.

Change from baseline and percent change from baseline for selected laboratory parameters over time

All analyses of laboratory data will use observed data regardless of insulin up-titration that occurs post-randomization. Visit windows are provided in Section 6.3 in order to link each laboratory test to a scheduled visit. Change from baseline during the short-term double-blind treatment period for selected laboratory parameters will be summarized by treatment group using descriptive statistics:

- hematocrit
- hemoglobin
- platelet count
- white blood cell (WBC) count
- Red blood cell (RBC) count
- total bilirubin
- alanine aminotransferase (ALT)
- alkaline phosphatase
- aspartate aminotransferase (AST)
- blood urea nitrogen (BUN)
- Measured creatinine clearance or estimated creatinine clearance (if measured creatinine clearance is not available) using the method of Cockcroft and Gault (change):

$$CrCl = \frac{(140 - \text{age}) \cdot (\text{weight in kg.}) \cdot (0.85 \text{ for females})}{\text{serum creatinine (mg/dL)} \cdot 72}$$

- creatine kinase (creatine phosphokinase) (CK)
- creatinine, serum (S_{cr})
- electrolytes - sodium, potassium, bicarbonate, chloride, magnesium and calcium
- total protein, serum
- albumin
- inorganic phosphorus
- albumin to creatinine ratio

- glucose:creatinine ratio
- spot urine for glucose
- triglycerides
- low-density lipoprotein cholesterol
- high-density lipoprotein cholesterol
- total cholesterol
- free fatty acid
- uric acid

Additional laboratory data summaries

A 24-week short-term double-blind treatment period, the following summaries will be provided.

Shift Tables for Electrolytes (Sodium, Potassium, Calcium, Phosphate, and Magnesium) Categories

Shift tables of Treated Subjects Data Set subjects with electrolytes values in categories of low, normal, and high (based on normal range of central laboratory) will be summarized by treatment group using the highest (for sodium, calcium, phosphate, and magnesium) and lowest (for sodium, potassium, and calcium) values (regardless of post-randomization insulin up-titration) obtained during the short-term double-blind treatment period.

Shift Tables for Urine Albumin Excretion Categories

Shift tables of Treated Subjects Data Set subjects with urine albumin to creatinine ratios in 0 - < 30mg/g (normoalbuminuria), 30 - < 300mg/g (microalbuminuria), and ≥ 300 mg/g (macroalbuminuria) will be summarized by treatment group using the Week 24 values (the last observation regardless of post-randomization insulin up-titration prior to Week 24 will be used if no Week 24 measurement is available).

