6.3 Longitudinal assessments

Day 1 for the short-term double-blind treatment period is the start date of double-blind treatment medication. The observation closest to the target day (and time where applicable) is the measurement used in the analysis for each scheduled visit.

The following visit window will apply for all laboratory parameters, vital signs and physical measurements in the short-term double-blind treatment period up to 24 weeks.

Table 9 Visit Windows for Short-term Double-blind Treatment Period Up to Week 24

Visit	Target Day	Day Range
Week 1	8	Post-baseline -11*
Week 2	15	12-22*
Week 4	29	23-43*
Week 8	57	44-71*
Week 12	85	72-106*
Week 18	127	107-148*

Table 9 Visit Windows for Short-term Double-blind Treatment Period Up to Week 24

Visit	Target Day	Day Range
Week 24	169	149 - Last day of double-blind treatment + 8 day for HbA1c, body weight, BMI, patient reported outcomes or 149 - Last day of double-blind treatment +1 day for insulin dose, CGM parameters, FPG, SMBG

* on or before the last day of double-blind treatment.

Table 10 Visit Windows for Short-term Double-blind Treatment Period Up to Week 24 for CGM parameters, Total daily Insulin and 6-point SMBG

Visit	Target Day	Day Range
Week 2	15	1-40*
Week 12	85	60-110*
Week 24	169	140- Last day of double-blind treatment

* on or before the last day of double-blind treatment.

The use of post double-blind treatment observations is specified in Section 6.4.

For all safety laboratory parameters, the use of post-double-blind treatment observations is specified in Section 4.2.4.5.

For laboratory and non-laboratory parameters, if a subject has more than one measurement included within a window, the assessment closest to the target day will be used. In case of ties between observations located on different sides of the target day, the earlier assessment will be used. In case of ties located on the same side of the target day (i.e. more than one value for the same day but different time), the value with the earlier entry date/time will be used.

For measurements referring to 24-hour collection periods (i.e. daily insulin dose) and those referring to multiple data collection points over multiple days (i.e. 6-point measurement parameters and CGM parameters) more than one value will be included in the analysis window. The value for analysis for the visit window will be calculated as the daily average of all available values for analysis for each parameter falling in the analysis window.

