9.3 Units and marked abnormality criteria for safety laboratory variables

Clinical laboratory variables will be summarized and listed using the units listed here. The criteria for marked abnormality for each variable are listed in the following table. Note that a

post-baseline lab value will be considered a MA only if it satisfies the specified criteria and is more extreme (farther from the limit) than is the baseline value.

Conventional (US) Units:

Clinical Laboratory variables	Units	Marked Abnormality Criteria	
		Low	High
Hematology			
HCT males/females	%	< 20.0%	> 55.0%
HCT males/females	%		> 60.0%
Hemoglobin males/females	g/dL	< 6 g/dL	> 18 g/dL
Hemoglobin males/females	g/dL		> 20 g/dL
Blood Chemistry			
Albumin	g/dL	≤ 2 g/dL	> 6 g/dL
Total protein	g/dL		> 10 g/dL
ALP	U/L		> 3X ULN
ALT	U/L		> 3X ULN
AST	U/L		> 3X ULN
ALT	U/L		> 5X ULN
AST	U/L		> 5X ULN
ALT	U/L		> 10X ULN
AST	U/L		> 10X ULN
ALT	U/L		> 20X ULN
AST	U/L		> 20X ULN
Total Bilirubin	mg/dL		> 1.5X ULN if PreRx ≤ ULN; > 2X ULN if PreRx > ULN
Glucose, Plasma Unspecified	mg/dL	< 54 mg/dL	> 350 mg/dL
Na (Sodium)	mEq/L	< 130 mEq/L	> 150 mEq/L
Na (Sodium)	mEq/L	< 120 mEq/L	
K (Potassium)	mEq/L	≤ 2.5 mEq/L	≥ 6.0 mEq/L
HCO3 (Bicarbonate)	mEq/L	≤ 13 mEq/L	
BUN	mg/dL		≥ 60 mg/dL
Creatinine	mg/dL		≥ 1.5X PreRx CREAT
Creatinine	mg/dL		≥ 2.5 mg/dL
CK (Creatine Kinase)	U/L		> 5X ULN
CK (Creatine Kinase)	U/L		> 10X ULN
Calcium	mg/dL	< 7.5 mg/dL	≥ 1 mg/dL from ULN and ≥ 0.5 mg/dL from PreRx CA

Clinical Laboratory variables	Units	Marked Abnormality Criteria	
		Low	High
Magnesium	mEq/L	< 1 mEq/L	> 4 mEq/L
PO4 (Phosphate)	mg/dL	Age 17-65: ≤ 1.8mg/dL Age ≥ 66: ≤ 2.1 mg/dL	Age 17-65: ≥ 5.6 mg/dL Age ≥ 66: ≥ 5.1 mg/dL
Urine			
UACR (Urinary Albumin to Creatinine Ratio)	mg/g		> 1800 mg/g

Standard International Units

Clinical Laboratory variables	Units	Marked Abnormality Criteria	
		Low	High
Hematology			
HCT males/females	vol	< 0.20	> 0.55
HCT males/females	vol		> 0.60
Hemoglobin males/females	g/L	< 60 g/L	> 180 g/L
Hemoglobin males/females	g/L		> 200 g/L
Blood Chemistry			
Albumin	g/L	≤ 20 g/L	> 60 g/dL
Total protein	g/L		> 100 g/dL
ALP	U/L		> 3X ULN
ALT	U/L		> 3X ULN
AST	U/L		> 3X ULN
ALT	U/L		> 5X ULN
AST	U/L		> 5X ULN
ALT	U/L		> 10X ULN
AST	U/L		> 10X ULN
ALT	U/L		> 20X ULN
AST	U/L		> 20X ULN
Total Bilirubin	μmol/L		> 1.5X ULN if PreRx ≤ ULN; > 2X ULN if PreRx > ULN
Glucose, Plasma Unspecified	mmol/L	< 3 mmol/L	> 19.4 mmol/L
Na (Sodium)	mmol/L	< 130 mmol/L	> 150 mmol/L

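### The electrolyte shift tables classify potassium only by its lowest value and phosphate and magnesium only by their highest, so transient high potassium, low phosphate and low magnesium do not show

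*SAP*

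**What the plan says.** Under the title "Shift Tables for Electrolytes (Sodium, Potassium, Calcium, Phosphate, and Magnesium) Categories", SAP section 4.2.4.5 puts treated subjects into "categories of low, normal, and high (based on normal range of central laboratory"). The on-treatment value for each subject is chosen "using the highest (for sodium, calcium, phosphate, and magnesium) and lowest (for sodium, potassium, and calcium) values", taken over all values "obtained during the short-term double-blind treatment period". The section gives no reason for treating the electrolytes differently.

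Three other parts of the SAP bear on the point:

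- **Marked abnormalities (section 4.2.4.5, Appendix 9.3).** These are summarized by treatment group, and "The direction of change (high or low) in MA will be indicated in the tables". The limits in the omitted directions are potassium ≥ 6.0 mEq/L; phosphate "Age 17-65: ≤ 1.8mg/dL", or ≤ 2.1 mg/dL from age 66; and magnesium < 1 mEq/L. For a subject with a marked abnormality, all values of that parameter are listed.
- **Change from baseline (section 4.2.4.5).** Potassium, magnesium and inorganic phosphorus are among the parameters summarized descriptively by treatment group.
- **Visit windows (section 6.3).** Table 9 has seven post-baseline windows. It is introduced with "The following visit window will apply for all laboratory parameters, vital signs and physical measurements", and it does not say at which visits electrolytes are drawn.

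**The concern.** A low/normal/high shift table invites the reader to take each column as the number of subjects who reached that category on treatment. For sodium and calcium that works, because each direction has its own extreme. For potassium the high column is filled from the subject's minimum, and for phosphate and magnesium the low column is filled from the maximum. A subject with one raised potassium among several normal values is placed in the normal column; if another value was low, in the low column. The raised value leaves no trace in the table.

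What is at stake is how three columns of a descriptive safety table are read. A nearly empty high-potassium column could be taken to mean that few subjects went above the normal range, when it shows only that few stayed above it at every measurement. No hypothesis test depends on these tables.

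**Working it through.** The SAP states no figure on this point, so there is none to reproduce. The check has a logical step, which needs no assumptions, and a size step, which does.

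**Step 1: logic.** Let a subject have k on-treatment values x₁, …, x_k.

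- Potassium: the subject is classified high if min(x₁, …, x_k) is above the upper normal limit, which is true only if all k values are above it.
- Phosphate and magnesium: the subject is classified low if max(x₁, …, x_k) is below the lower normal limit, which is true only if all k values are below it.
- A table built on the matching extreme would count the subject if at least one value is beyond the limit.

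Hence the share of affected subjects that the planned table does not show is

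share missed = 1 − P(all k beyond the limit) / P(at least one beyond the limit).

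For k = 1 the two probabilities are equal and the share missed is 0.

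**Step 2: size, on assumptions.** The SAP gives neither the number of electrolyte values per subject, nor how often a value is out of range, nor the within-subject correlation. Assumed:

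- k from 1 to 7 (seven is the number of Table 9 windows, so an upper case for scheduled visits)
- 2.5% of single values beyond the limit in the omitted direction
- normally distributed values with a subject-level random intercept and intraclass correlation (ICC) 0.5 to 0.9

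Simulating 1,000,000 subjects gives the following; direct numerical integration of the same model agrees to within 0.3 percentage points on the share missed.

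| k | ICC | At least one beyond | All beyond | Share missed |
|---|---|---|---|---|
| 7 | 0.5 | 11.45% | 0.016% | 99.9% |
| 7 | 0.8 | 7.45% | 0.30% | 96.0% |
| 7 | 0.9 | 5.70% | 0.684% | 88.0% |
| 4 | 0.5 | 7.77% | 0.073% | 99.1% |
| 4 | 0.8 | 5.73% | 0.519% | 90.9% |
| 4 | 0.9 | 4.68% | 0.941% | 79.9% |
| 2 | 0.5 | 4.50% | 0.46% | 89.8% |
| 2 | 0.8 | 3.94% | 1.112% | 71.8% |
| 2 | 0.9 | 3.52% | 1.471% | 58.2% |
| 1 | any | 2.5% | 2.5% | 0% |

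Worked example, k = 4 and ICC 0.8: 1 − 0.519/5.73 = 0.909.

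Sensitivity to the assumed rate, for k = 4 and ICC 0.8: with 1% of single values beyond the limit, 1 − 0.158/2.48 = 93.6%; with 5%, 1 − 1.312/10.64 = 87.7%. The share missed is driven more by the number of values and their correlation than by the rate.

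**Step 3: what other outputs cover.**

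| Value in the omitted direction | Where it shows |
|---|---|
| Beyond the marked-abnormality limit | Marked-abnormality summary by direction, plus the listing |
| Shift in the group mean | Change-from-baseline summary |
| Between the normal limit and the marked-abnormality limit, at some visits only | No categorical laboratory summary |
| Beyond the normal limit at every measurement | The planned shift table |

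**The case against.** The strongest reply is that this is a choice and not a mistake. The sentence names a direction for each electrolyte, can be programmed as written, and is contradicted nowhere. A table in one direction can be a deliberate display of the change of most interest. That stands as far as it goes: nothing shows the choice was unintended. It does not explain why a one-direction table keeps all three categories, or why no reason is given.

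A second reply is that other outputs cover the omitted directions. This is largely right. Marked values, group mean shifts and abnormalities reported as adverse events all appear elsewhere. What remains is the count of subjects with milder, intermittent excursions, and that count is what a normal-range shift table is for.

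Three stronger readings are tempting, and the SAP does not support them:

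- **That the tables miss nearly every affected subject.** This needs about four or more values per subject and only moderate persistence. Table 9 assigns measurements to windows and is not a sampling schedule. Treating repeated values as independent is the extreme case. Subjects with a single value are classified correctly, and persistent abnormality is the kind least likely to be missed.
- **That high potassium would go unseen whatever the drug does.** Sustained elevation would show in this table, marked elevation in the marked-abnormality summary, and a mean shift in the change summaries. A link from the separate ACE-inhibitor/ARB summary, or from the adverse events of special interest, to high potassium is one a reader might draw; the SAP does not draw it.
- **That Appendix 9.3 contradicts the shift tables because its limits are two-sided.** Appendix 9.3 also gives two-sided limits for hematocrit, hemoglobin, albumin and glucose, for which section 4.2.4.5 plans no such shift table. Two-sided limits there do not imply two-sided shift tables.

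**Conclusion.** The point holds for the shift tables only. The high column for potassium and the low columns for phosphate and magnesium count subjects with several values only if every on-treatment value was beyond the limit; this follows from the SAP's own rule. The size is conditional. With 2.5% of single values beyond the limit, about 91-99% of affected subjects are missed with four values (ICC 0.5-0.8), about 58-90% with two (ICC 0.5-0.9), and none with one. The rate, number of values and ICC are all assumptions.

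The information lost is the count of subjects whose most extreme value in the omitted direction lies between the normal limit and the marked-abnormality limit. This is a minor, inexpensive improvement to descriptive safety reporting. It does not touch the efficacy analyses or type I error, and it is not evidence that a safety signal would be hidden.

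**What to change.** In the electrolyte shift-table paragraph of section 4.2.4.5, specify both the highest and the lowest on-treatment value for potassium, phosphate and magnesium, as is already done for sodium and calcium. Each electrolyte then has one table from the lowest value and one from the highest.

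The cost is one amended sentence and three more descriptive tables (highest potassium, lowest phosphate, lowest magnesium), using laboratory data that the planned tables already draw on. The drawback is a longer table set.

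If a single direction is intended, state that with the reason, and label each table with the extreme used so that the opposite category is not read as a count of subjects who ever reached it. This costs no extra tables but leaves the mild excursions uncounted.

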4.2.4.6 Vital signs

Vital signs data obtained after the start of study medication dosing up to and including 4 days after the last short-term double-blind dosing date or up to the start of the long-term treatment period, whichever comes first, will be considered as obtained during the short-term double-blind treatment period.

Visit windows are provided in Section 6.3 in order to link each vital sign measurement to a scheduled visit. Measured values and changes from baseline in vital sign measurements will be summarized by treatment group at each scheduled visit using descriptive statistics (using available data regardless of insulin up-titration for subjects in Treated Subjects Data Set).

4.2.4.7 Physical examination

All physical examination data and abnormalities will be listed. Shift tables from baseline to end of short-term double blind treatment period of normal vs. abnormal assessments will be

provided (the last observation regardless of rescue prior to week 24 will be used if no week 24 measurement is available).

4.2.4.8 Electrocardiograms

The normality/abnormality of the ECG tracing, as determined by the investigator, will be summarized using frequency tables on number of subjects who have a normal/abnormal ECG tracing at Week 24 of the short-term double-blind treatment period, overall and by the ECG tracing at baseline. When the data at Week 24 is not available for a discontinued subject, then the last observation before discontinuation of that subject (regardless of insulin up-titration) will be used for summary.

4.2.4.9 Pregnancy test results

By-subject listing of pregnancy test results will be provided using Safety Analysis Set.

5. INTERIM ANALYSES

No interim analysis is planned for this study.

6. CONVENTIONS

6.1 Duration of type 1 diabetes

Duration of T1DM is calculated as the number of years from the T1DM diagnosis date to informed consent date:

$$(I + \text{consent date} - \text{diagnosis date}) / 365.25.$$

The duration of diabetes will be included in the baseline diabetes characteristics listing.

If the date T1DM was diagnosed is partially missing, the following rules will take effect:

- Missing day, but month and year are present: the day will be imputed as the 15th day of the month.
- Missing day and month, but year is present: the day and month will be imputed as 30 June of the year (provided that the imputed date is less than the consent date).
- Missing year, but day and month are present: No imputations will occur, and the subject will be excluded from all summaries related to duration of T1DM.
- Missing day, month and year: No imputations will occur, and the subject will be excluded from all summaries related to duration of T1DM.
- If any such imputed date falls after the consent date, then the diagnosis date will be taken as equal to the consent date.

These durations, even if partially imputed, will be listed. However, only the portion of the date of diagnosis actually observed, rather than imputed dates, will be displayed in listings.

6.2 Missing and multiple measurements

For listings of efficacy, safety, outcome research measures, missing values will be represented as not reported.

For all analyses and summaries of efficacy, safety, outcome research measures, missing values will not be imputed, except those specified to be analyzed using LOCF methodology, that are imputed by the LOCF.

For HFS-II worry subscale, an item mean score will be used to impute the summary score if more than 75% of items have responses (i.e., at least 14 out of 18 items have responses). Instead of dividing by the entire subscale to compute the item mean, only divide by the number of questions answered. The item mean score is converted to summary score by multiplying 18. If less than 14 items are available, the summary score will be counted as missing.

Some laboratory samples may be inadvertently analyzed multiple times for the same test, producing multiple lab results on the same collection date and time for the same subject. The selection of laboratory result for analysis for this subject will follow AZ global standard.

If the blood pressure measurements are taken at a wrong position, e.g., sitting instead of standing, then these measurements will be excluded from the summary/analysis.

